## 8 STUDY ASSESSMENTS AND PROCEDURES

### 8.1 EFFICACY AND SAFETY ASSESSMENTS

This is an observational non-interventional study, therefore there is no evaluation of efficacy or safety. Blood will be taken prior to discharge from the hospital for the index MI event (see separate Laboratory Sample Manual for details on sample collection, storage, and shipment to a core laboratory) and will be used to quantify FcγRIIa. Blood can be taken up to 2 weeks post-study enrollment. Risks associated with phlebotomy include discomfort, bleeding, and a remote risk of infection.

Subjects will receive medications as determined by their health care provider and as part of regular standard of care. Subjects will be followed throughout the duration of the study to assess for study endpoints including MI, stroke, death, and bleeding events (BARC type 2-5). Subjects who experience an endpoint event will continue to be followed throughout the entire study and any subsequent events will also be confirmed and recorded.

### 8.2 ADVERSE EVENTS AND SERIOUS ADVERSE EVENTS

#### 8.2.1 DEFINITION OF ADVERSE EVENTS (AE)

Because this is a non-interventional study and only phlebotomy, a commonly performed procedure, will be performed, an adverse event for this study is defined as any untoward

medical occurrence associated with venipuncture. Given the routine nature of phlebotomy, only those AEs that meet the criteria for serious will be required to be reported and followed to resolution or until considered stable.

For this study, stroke, MI, death, and bleeding events will be reported as endpoint events and will not be considered or reported as adverse events.

### 8.2.2 DEFINITION OF SERIOUS ADVERSE EVENTS (SAE)

An AE is considered "serious" if it results in any of the following outcomes: death, a life-threatening adverse event, inpatient hospitalization or prolongation of existing hospitalization, a persistent or significant incapacity or a congenital anomaly/birth defect. Important medical events that may not result in death, be life-threatening, or require hospitalization may be considered serious when, based upon appropriate medical judgment, they may jeopardize the participant and may require medical or surgical intervention to prevent one of the outcomes listed in this definition.

For this study, only SAEs related to phlebotomy will be reported.

### 8.2.3 CLASSIFICATION OF AN ADVERSE EVENT

#### 8.2.3.1 SEVERITY OF EVENT

The following definitions will be used to describe severity of an SAE:

- **Mild** – Events require minimal or no treatment and do not interfere with the subject's daily activities.
- **Moderate** – Events result in a low level of inconvenience or concern. Moderate events may cause some interference with functioning.
- **Severe** – Events interrupt a subject's usual daily activity and may require systemic drug therapy or other treatment.

#### 8.2.3.2 RELATIONSHIP TO STUDY PROCEDURE

All SAEs related to phlebotomy must have their relationship to this procedure assessed by the investigator who will evaluate the event based on temporal relationship and clinical judgment.

- **Related** – The event is known to occur with the study procedure, there is a reasonable possibility that the study procedure caused the SAE, or there is a temporal relationship between the study procedure and event. Reasonable possibility means that there is evidence to suggest a causal relationship between the study procedure and the SAE.
- **Not Related** – There is not a reasonable possibility that the study procedure caused the event, there is no temporal relationship between the study procedure and event onset, or an alternate etiology has been established.

#### 8.2.4 SERIOUS ADVERSE EVENT ASSESSMENT AND FOLLOW-UP

All SAEs will be captured in the CRF. Information to be collected includes event description, investigator's assessment of severity, relationship to study procedure, and resolution/stabilization date. All SAEs will be followed to resolution or until considered stable.

#### 8.2.5 SERIOUS ADVERSE EVENT REPORTING

Investigators will monitor subjects for SAEs related to phlebotomy and must immediately report an SAE to the sponsor. In the event a subject experiences a Suspected Unexpected Serious Adverse Reaction (SUSAR) due to venipuncture, the sponsor must notify the Food and Drug Administration (FDA) and all participating investigators of this safety report, as soon as possible, but in no case later than 15 calendar days after the sponsor determines that the information qualifies for reporting. Furthermore, the sponsor must also notify FDA of any unexpected fatal or life-threatening suspected adverse reaction as soon as possible but in no case later than 7 calendar days after the sponsor's initial receipt of the information.

#### 8.2.6 DATA SAFETY MONITORING

Because of the limited risk of this non-interventional trial, data safety and monitoring will be managed without a formal data safety and monitoring committee. Investigators at each site will report SAEs related to study procedures (only phlebotomy) to the sponsor. The sponsor will bring SAEs to the attention of the co-principal investigators, [name] and [name] (see Section 10.5). Drs. [name] and [name] will be primarily responsible for the oversight of data and safety.

### 9 STATISTICAL CONSIDERATIONS

#### 9.1 STATISTICAL HYPOTHESES

Specifically, the study hypotheses are:

1. Platelet expression of FcγRIIa is associated with risk of MI, stroke, and death.
2. Incorporating platelet expression of FcγRIIa into existing risk scores improves identification of patients at high risk of MI, stroke, and death.
3. Platelet expression of FcγRIIa is not associated with risk of major bleeding.

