and older age ([name] 2018), there will not be a significantly increased incidence of clinically significant bleeding, defined as BARC type 2-5, among patients with high platelet expression of FcγRIIa.

Lastly, to ensure consistent results, platelet expression of FcγRIIa will be quantified at a core laboratory. At clinical sites, citrate anticoagulated blood will be added to fixative tubes. These tubes will be shipped to the core laboratory for quantification of platelet FcγRIIa expression.

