## 3 OBJECTIVES AND ENDPOINTS

The primary objective of the study is to determine whether platelet expression of FcγRIIa is associated with risk of MI, stroke, and death.

Secondary objectives are

- Develop a score that combines clinical characteristics plus platelet expression of FcγRIIa to determine the risk of MI, stroke, and death.
- Determine whether platelet expression of FcγRIIa is associated with risk of major bleeding.

The primary endpoint is the composite of death, MI, and stroke. A secondary endpoint is clinically significant bleeding according to BARC type 2-5.

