#### 9.2 SAMPLE SIZE DETERMINATION

This study is designed to provide a sufficient number of events to build and evaluate a prediction model. The planned sample size of 800 subjects will continue until at least 80 ischemic events have occurred. Under the guideline from Steyerberg of 10 events required per predictor (Steyerberg 2019), this sample size will allow a model with FcγRIIa and up to seven additional predictors to be built. Preliminary results ([name] 2018) suggest that a 4-fold greater incidence of events will be seen in subjects with high platelet expression of FcγRIIa. For

the primary endpoint, there will be at least 95% power to detect a 2-fold greater incidence of cardiovascular endpoints (MI, stroke, and death) with a two-sided  $\alpha < 0.01$  assuming 8% of subjects experience the endpoint. With the planned sample size of 800 a hazard ratio (HR) of 1.9 with a  $p=0.04$  (lower bound of the 95% CI of 1.2) can be detected. For the secondary endpoint, there will be 95% power to detect a hazard ratio of 1.93 when comparing bleeding risk in subjects with high compared with low FcγRIIa expression when assuming a two-sided  $\alpha=0.05$  and 5% of subjects experience bleeding in the low FcγRIIa expression group.

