#### 9.4.3 ANALYSIS OF THE SECONDARY OBJECTIVES

First Secondary Objective: Negative predictive value, positive predictive value, sensitivity, and specificity will be calculated. Prediction will be performed using a Cox regression model with the following predictors: platelet expression of FcγRIIa, sex, age, MVD, CKD, DM, and prior MI. Evaluation of the model's error rates will be based on a leave-one-out cross-validation approach. Additional models will evaluate the performance of the predictive model using a continuous measure of FcγRIIa with the performance of predictive models using various binary measures of FcγRIIa.

Second Secondary Objective: The adjusted Cox proportional hazards model described for the primary objective analysis will be used to compare the bleeding risk as a function of FcγRIIa expression, both as a continuous and as a binary variable.

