5.7.2 Analysis of the Secondary Objective

First Secondary Objective: Negative predictive value, positive predictive value, sensitivity, and specificity will be calculated. Prediction will be performed using a Cox regression model with the following predictors: platelet expression of Fc γ RIIa, sex, age, and clinical risk factors associated with increased cardiovascular risk. Evaluation of the model's error rates will be based on a leave-one-out cross-validation approach. Additional models will evaluate the performance of the predictive model using a continuous measure of Fc γ RIIa with the performance of predictive models using various binary measures of Fc γ RIIa.

Second Secondary Objective: The adjusted Cox proportional hazards model described for the primary objective analysis will be used to compare the bleeding risk as a function of Fc γ RIIa expression. One

model will include FcγRIIa as a continuous variable, and another using the dichotomized version of FcγRIIa selected as the optimal version for risk stratification.

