5.10 Determination of Sample Size

This study is designed to provide a sufficient number of events to build and evaluate a prediction model. The planned sample size of 800 subjects will continue until at least 80 ischemic events have occurred. Under the guideline from Steyerberg of 10 events required per predictor (Steyerberg 2019), this sample size will allow a model with FcγRIIa and up to seven additional predictors to be built. Preliminary results ([name] 2018) suggest that a 4-fold greater incidence of events will be seen in subjects with high platelet expression of FcγRIIa. For the primary endpoint, there will be at least 95% power to detect a 2-fold greater incidence of cardiovascular endpoints (MI, stroke, and death) with a two-sided $\alpha < 0.01$ assuming 8% of subjects experience the endpoint. With the planned sample size of 800 a hazard ratio (HR) of 1.9 with a $p=0.04$ (lower bound of the 95% CI of 1.2) can be detected. For the secondary endpoint, there will be 95% power to detect a hazard ratio of 1.93 when comparing bleeding risk in subjects with high compared with low FcγRIIa expression when assuming a two-sided $\alpha = 0.05$ and 5% of subjects experience bleeding in the low FcγRIIa expression group.

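### Hypothesis 3 says FcγRIIa is not associated with bleeding, but the plan has only a test for a difference and no margin or interval rule that could support that statement

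*Protocol*

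**What the plan says.** - **Hypothesis.** Protocol 9.1, repeating 2.2, lists as its third hypothesis that "Platelet expression of FcγRIIa is not associated with risk of major bleeding".
- **Objective.** Protocol 3 is neutral: "Determine whether platelet expression of FcγRIIa is associated with risk of major bleeding". SAP 5.6 repeats the objective. SAP 5.1 to 5.10 do not restate the hypothesis.
- **Expectation.** The background (Protocol 2.3, Current Study) anticipates that, among patients with high expression, "there will not be a significantly increased incidence of clinically significant bleeding, defined as BARC type 2-5".
- **Analysis.** SAP 5.7.2: "The adjusted Cox proportional hazards model described for the primary objective analysis will be used to compare the bleeding risk". One model takes FcγRIIa as continuous. The other uses the dichotomy chosen as optimal for risk stratification. Protocol 9.4.3 likewise plans a continuous and a binary form.
- **Sizing.** Protocol 9.2 and SAP 5.10 state that "there will be 95% power to detect a hazard ratio of 1.93" for high against low expression, at two-sided 5%, with 5% of the low group bleeding. No time unit is attached to the 5%.
- **Decision rule.** SAP 5.7.1 gives one for the primary endpoint only (two-sided p below 0.05 means associated). Neither document gives one for bleeding.

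**The concern.** A hypothesis of no association is supported by showing that the interval for the effect excludes every association large enough to matter. The plan names no such size. Its Cox test takes no association as the null, so the result is either a rejection of Hypothesis 3 or a failure to reject it. A failure to reject may simply reflect few events.

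This matters because low bleeding risk is part of the marker's proposed value. Protocol 2.3 suggests that FcγRIIa may separate thrombotic from bleeding risk. Protocol 2.1 argues that high-risk patients should gain more from longer, stronger antiplatelet therapy. The results are meant to support a later trial. The background already cites the absence of a bleeding association in a 197-patient pilot as supporting evidence, so a non-significant result here could well be used in the same way.

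**Working it through.** **Inputs from the documents.** N = 800; two-sided alpha 0.05; 5% bleeding in the low group; HR 1.93; about 12 months of accrual and at least 18 months of follow-up for the last subject.

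**Assumptions.** Even high/low split (the pilot had 55% high in the increased-risk group, which changes little); proportional hazards; no power lost to covariates. Uniform accrual gives a mean follow-up of about 24 months, so an annual 5% is about 10% cumulative. The continuous model cannot be sized, because no FcγRIIa standard deviation is given.

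**Formulas.** Low-group risk is p.
- Expected events D = 400p + 400[1 − (1 − p)^HR]
- SE(log HR) = 2/√D
- Power ≈ Φ(ln HR/SE − 1.96)

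**The plan's own figure.** For 95% power at HR 1.93, D = 4(1.96 + 1.645)²/(ln 1.93)² ≈ 121 events. With p = 0.05, D = 20 + 400 × 0.0943 = 57.7, SE = 0.263 and power is about 70%, so the stated 95% is not reproduced. With p = 0.10, D = 113.6 and power is about 94%. The time unit of the 5% therefore matters, and both readings are carried forward.

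**Chance of p>0.05 when the true HR is 1.5** (ln 1.5 = 0.405)

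| Reading | Events | SE | Power | Non-significant |
|---|---|---|---|---|
| 5% in total | 20 + 400 × 0.0741 = 49.6 | 0.284 | 30% | 70% |
| 5% per year (about 10% cumulative) | 40 + 400 × 0.1462 = 98.5 | 0.202 | 52% | 48% |
| 120 events | 120 | 0.183 | 60% | 40% |

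A simulation of 20,000 trials gave 72% for the first row and 49% for the second. With about 50 events, any observed HR from 1 up to exp(1.96 × 0.284) ≈ 1.74 is non-significant.

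**What showing no association would take.** The documents give no margin, so 1.5 is illustrative. The true HR is taken as 1.
- Upper 95% limit below 1.5 with 80% power: 4(1.96 + 0.842)²/(0.405)² ≈ 191 events.
- 90% interval within 1/1.5 to 1.5 with 80% power: 4(1.645 + 1.282)²/(0.405)² ≈ 209 events.
- Expected at HR 1: 800 × 0.05 = 40 to 800 × 0.10 = 80 events. The chance that the upper 95% limit falls below 1.5 is then about 25% to 44%.

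**Whether 1.93 could serve as the bound.** If the true HR is 1.5, the chance that the upper limit falls below 1.93 is Φ([ln 1.93 − ln 1.5]/SE − 1.96). This is about 14% with 50 events and 28% with 120. Such a rule would declare support for no association in those shares of studies despite a real 50% increase.

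**The case against.** The strongest reply is that the plan never commits the error. A reader might infer that p>0.05 is the planned confirmation of Hypothesis 3, but no section says so. A reader might also take the Protocol 2.3 sentence as a success criterion. It is introduced as something anticipated, in a background section, and is a forecast. The bleeding objective is open, and a neutral objective would not by itself need a margin. SAP 5.7.2 carries the primary Cox model over to bleeding, and SAP 5.7.1 names a point estimate, confidence interval and p-value as that model's outputs. The interval would therefore presumably be reported, and what is missing is a rule for reading it.

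The size also depends on the undated 5%. Quoting 70% alone would give only the unfavourable end. Finally, this is a secondary endpoint in a study that does not alter care.

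All of this stands and narrows the point. It does not remove it: Hypothesis 3 is listed under statistical hypotheses, and the plan contains no analysis that could support it.

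**Conclusion.** The point holds as a mismatch between a stated hypothesis and the analysis attached to it. It does not hold as a claim that the sponsor has adopted non-significance as proof. A non-significant bleeding result would be weak evidence: a true 50% increase would go undetected in about 70% of studies on the literal 5%, 48% if 5% is annual, and 40% with 120 events. These figures rest on an unadjusted, evenly split high/low comparison of 800 subjects. Adjustment would usually lower power.

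A reader might also infer that 1.93 is the plan's tolerance for excess bleeding. The documents present it only as an effect the study has power to detect, so it should not become the margin by default. The change is worth making, in proportion to a secondary hypothesis.

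**What to change.** In Protocol 9.1 and SAP 5.7.2, choose one of two options.

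- **(a) Estimation.** Restate Hypothesis 3 as estimating the association. Report the bleeding HR with its 95% confidence interval, and state that a non-significant result means association is neither shown nor excluded.
- **(b) Keep the hypothesis.** Call it supported only if the confidence interval, at a stated level, for the high-versus-low HR lies within a two-sided margin. The sponsor should justify that margin clinically and not take 1.93 by default. Use a cut fixed in advance; the SAP's 1,750 is available. State the chance of meeting the rule. Two-sided matters because not associated also excludes a clear inverse association, and Protocol 2.3 cites lower bleeding with high platelet reactivity.

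**Cost.** Option (a) is wording only. Option (b) may add one model, because the binary bleeding model in SAP 5.7.2 uses the cut selected as optimal, which may not be 1,750. A favourable no-bleeding claim becomes harder: even the one-sided part of a 1.5 margin needs about 191 events for 80% power at a true HR of 1, against about 40 to 80 expected. Unless the sponsor can defend a wider margin, option (a) fits the planned data better.

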#### 9.2 SAMPLE SIZE DETERMINATION

This study is designed to provide a sufficient number of events to build and evaluate a prediction model. The planned sample size of 800 subjects will continue until at least 80 ischemic events have occurred. Under the guideline from Steyerberg of 10 events required per predictor (Steyerberg 2019), this sample size will allow a model with FcγRIIa and up to seven additional predictors to be built. Preliminary results ([name] 2018) suggest that a 4-fold greater incidence of events will be seen in subjects with high platelet expression of FcγRIIa. For

the primary endpoint, there will be at least 95% power to detect a 2-fold greater incidence of cardiovascular endpoints (MI, stroke, and death) with a two-sided  $\alpha < 0.01$  assuming 8% of subjects experience the endpoint. With the planned sample size of 800 a hazard ratio (HR) of 1.9 with a  $p=0.04$  (lower bound of the 95% CI of 1.2) can be detected. For the secondary endpoint, there will be 95% power to detect a hazard ratio of 1.93 when comparing bleeding risk in subjects with high compared with low FcγRIIa expression when assuming a two-sided  $\alpha=0.05$  and 5% of subjects experience bleeding in the low FcγRIIa expression group.

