### **Current Study**

Confirmation of results seen in the single center pilot study is necessary in a larger multicenter trial to validate the results of the pilot study and to determine whether platelet expression of FcγRIIa can be used to guide individualized precision therapy and improve outcomes. Results from the current study will determine the prognostic implications of platelet FcγRIIa expression as well as the optimal manner in which to use platelet FcγRIIa expression. The analysis plan will include assessment of platelet FcγRIIa expression as a continuous variable as well as a sensitivity analysis designed to determine whether FcγRIIa  $\geq 11,000/\text{platelet}$  is the optimal threshold for discrimination of risk. In addition, it will provide key preliminary evidence regarding prognostic implications of platelet FcγRIIa expression associated with anti-thrombotic regimens and support plans for a subsequent clinical trial designed to use platelet FcγRIIa expression as a precision tool.

To identify subjects at greater risk of events, subjects will be enrolled who have an increased risk of cardiovascular events based on results from the SWEDEHEART registry that analyzed 100,879 patients (Lindholm 2019). Hospitalized MI subjects with  $\geq 2$  of the following risk factors; age  $\geq 65$ , prior MI, diabetes mellitus, multivessel coronary artery disease (two or more vessels or left main with a stenosis  $\geq 50\%$  at coronary angiography) and chronic kidney disease (an estimated glomerular filtration rate below  $60 \text{ ml/min}/1.73 \text{ m}^2$ ) will be enrolled in the current study. In the SWEDEHEART registry, patients with  $\geq 2$  risk factors comprised 47% of patients and their risk of death, MI and stroke was 9.7/100 patient years. In the pilot study, 55% of subjects with increased risk based on clinical risk scores exhibited platelet expression of FcγRIIa  $\geq 11,000$  ([name] 2020). In the current study, enrollment of subjects receiving treatment with anticoagulant therapy (i.e., for treatment of atrial fibrillation, venous thromboembolism) will be limited to approximately 100 subjects. Subjects with non-cardiovascular conditions expected to limit survival to less than 2 years will be excluded in the current study.

Because high platelet expression of FcγRIIa increases platelet reactivity (Boylan 2008, Lova 2002), it is anticipated that despite an association between high platelet expression of FcγRIIa

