The primary endpoint will be the composite of death, MI, and stroke. MI will be defined in accordance with the 4th universal definition (Thygesen 2018) and stroke consistent with consensus guidelines (Sacco 2013). The incidence of clinically significant bleeding will be determined using the Bleeding Academic Research Consortium (BARC) scale (Mehran 2011) and is defined as BARC type 2-5. Study endpoint events will be confirmed by the review of medical records by the investigator and all relevant medical records will be obtained by the site for submission to the sponsor (as described in Section 10.8). Subjects who experience an endpoint event will continue to be followed throughout the entire study and any subsequent endpoint events will also be confirmed and recorded. See Appendix 1 for study endpoint event definitions.

A total of approximately 800 subjects will be enrolled at approximately 10-20 sites in the US. It is anticipated that it will take about 12 months to enroll the total number of subjects. The study and subject follow-up will continue until 1) at least 80 ischemic events (MI, stroke, and death) have occurred, and 2) the last subject enrolled has completed at least 18 months of follow-up. Based on an annual ischemic event rate of 10%, the overall length of participation in the study is anticipated to be up to 3 years. Results will be monitored during the course of the study.

Figure 5 Schematic Overview of the Study

MI=myocardial infarction; NSTEMI= non-ST-segment elevation MI, STEMI= ST-segment elevation MI

\* Subjects who experience an endpoint event will continue to be followed throughout the entire study and any subsequent events will also be confirmed and recorded.

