5.7 Statistical Methods

5.7.1 Analysis of the Primary Objective

The primary analysis of the primary endpoint will be a Cox proportional hazards model. The dependent variable is the number of days from enrolment to the occurrence of a primary endpoint, with censoring at the last day of complete follow-up; independent variables will be FcγRIIa (measured in thousands), age in years, history of diabetes mellitus, prior revascularization, multi-vessel coronary artery disease (MVD) defined as ≥2 vessels or left main with a stenosis ≥50%, chronic kidney disease (CKD) defined as estimated glomerular filtration rate (GFR) < 60 ml/min/1.73 m², prior MI, hypertension, tobacco use, heart failure or LVEF<30%, previous stroke or transient ischemic attack, and peripheral arterial disease. Interest is in the FcγRIIa parameter: point estimate (increase in risk per 1000-unit increase in FcγRIIa), confidence interval and p-value. FcγRIIa will be declared to be associated with cardiovascular risk if the 2-sided p-value from this model is < 0.05.

A set of exploratory/sensitivity and subgroup analyses based on the Cox model will also be conducted.

- Instead of censoring at the last day of complete follow-up, censor at the last day of vital status follow-up
- FcγRIIa as the only covariate in the model
- Separate analyses of each component of the primary endpoint: MI and stroke, both censored at the last day of complete follow-up, and death, censored at the last day of vital status follow-up
- Run the primary model in subgroups defined by age (in decades), sex, history of diabetes and prior revascularization (including all covariates except the subgroup variable in the model)
- Run the primary model with the use of DAPT (any use prior to a primary endpoint), and its interaction with FcγRIIa, as additional covariates

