A nearly perfect fit is obtained with log-transformation of the data. The plotted values are the natural logs of the original values. This regression line also doesn't go through zero (see the expanded scale), so the regression line is as follows: $\log(\text{Quantibrite}) = a * \log(\text{Original Bangs}) + b$, where $a = 0.9160084$ and $b = -1.0611595$.

The relationship derived was used to translate the original threshold of 11,000 to a new threshold that will be tested in this study. A value of 11,000 obtained with the original calculation template provided by Bangs Beads corresponds to a Quantibrite value of $\exp(a * \log(11,000) + b) = 1742.183$. Thus, we will use a threshold rounded to the closest 50, or 1,750, to define subjects with low versus high Fc γ RIIa.

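### The stated 95% power for a bleeding hazard ratio of 1.93 does not follow from the stated inputs, which give about 70%; the time base of the 5% and the high/low split are missing

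*Protocol*

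**What the plan says.** Protocol 9.2, repeated in SAP 5.10, claims for bleeding that "there will be 95% power to detect a hazard ratio of 1.93 when comparing bleeding risk in subjects with high compared with low" FcγRIIa expression. The inputs given are a two-sided alpha of 0.05, 800 planned subjects, and an assumption that "5% of subjects experience bleeding in the low" group. Neither section gives the period to which the 5% applies, the assumed share of subjects with high expression, the expected number of bleeding events, or the formula.

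The only nearby figure for the split is in Protocol 2.3 (Current Study), where in the pilot "55% of subjects with increased risk based on clinical risk scores exhibited platelet expression of" FcγRIIa at or above 11,000. The power text does not use it.

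Three other passages bear on how the bleeding result will be used:

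- The third hypothesis in Protocol 9.1 is that expression "is not associated with risk of major bleeding".
- The only decision rule in the SAP (5.7.1) concerns the primary endpoint: FcγRIIa "will be declared to be associated with cardiovascular risk if the 2-sided p-value from this model is < 0.05".
- SAP 5.7.1 also fixes a cut in the re-scaled units: "Thus, we will use a threshold rounded to the closest 50, or 1,750, to define subjects with low versus high" expression. SAP 5.7.2, however, plans the dichotomised bleeding model at the version "selected as the optimal version for risk stratification".

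**The concern.** A sample-size statement should be reproducible from its own inputs. An overall bleeding proportion of roughly 7% in 800 subjects yields too few events for 95% power at a hazard ratio below 2.

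This matters more than usual because the hypothesis is one of no association. Readers of a null bleeding result will look to the power statement to judge how much reassurance it gives. If the true figure is about 70%, a bleeding hazard ratio of 1.93 would be missed about three times in ten, not one in twenty. The SAP does not say how a non-significant bleeding result is to be interpreted, so such a result could be reported as confirming the hypothesis, backed by a power figure that the inputs do not support.

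**Working it through.** **Inputs.** From Protocol 9.2 and SAP 5.10: N = 800, low-group proportion 5%, HR 1.93, two-sided alpha 0.05, stated power 95%. The split is not given there; I assume 50/50 and show a range. From Protocol 4.1: enrollment of about 12 months and at least 18 months of follow-up for the last subject.

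**Literal reading (5% of low-group subjects bleed over the study).**

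- High-group proportion under proportional hazards: 1 − 0.95^1.93 = 9.43%.
- Expected events at 50/50: 400 × (0.05 + 0.0943) = 57.7.
- Schoenfeld power: Φ(√(57.7 × 0.25) × ln 1.93 − 1.96) = Φ(3.80 × 0.6575 − 1.96) = Φ(0.54) = 70.4%.
- Events needed for 95%: (1.96 + 1.645)² / (0.25 × 0.6575²) = 120.

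**The 95% is not recovered by changing the split or the method.**

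| Variant (5% over the study) | Events | Power |
|---|---|---|
| 40% high, Schoenfeld | 54.2 | 65.9% |
| 45% high, Schoenfeld | 55.9 | 68.7% |
| 55% high, Schoenfeld | 59.5 | 71.3% |
| 60% high, Schoenfeld | 61.2 | 71.3% |
| 50/50, Freedman | 57.7 | 67.4% |
| 50/50, two proportions | – | 67.8% |
| 50/50, two proportions, 1.93 as a risk ratio | – | 71.4% |
| 50/50, two proportions, 1.93 as an odds ratio | – | 64.2% |
| 50/50, Schoenfeld, one-sided 0.05 | 57.7 | 80.3% |

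**What would give 95% with 800 subjects at 50/50.**

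- A low-group proportion of about 10.6%: the high group is then 1 − 0.894^1.93 = 19.45%, and events are 400 × (0.106 + 0.1945) = 120. The figure is 11.1% at 45% high and 10.4% at 55% high.
- Or, keeping 5%, an HR of about 2.42: 66.7 events, Φ(√(66.7 × 0.25) × ln 2.42 − 1.96) = 95%. The range is 2.46 to 2.39 for 45% to 55% high.

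**Readings that come close to 95% but are not written.**

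- *5% per year.* Mean follow-up is 18 + 12/2 = 24 months. The low-group proportion is 1 − 0.95² = 9.75% and the high-group proportion is 1 − 0.9025^1.93 = 17.96%. Events are 400 × (0.0975 + 0.1796) = 110.8, and power is 93.3% (92.4% to 93.8% for 45% to 55% high). At 2.25 years there are 123.5 events and power is 95.5%.
- *800 per group.* Events are 800 × 0.1443 = 115.4, and power is 94.2%.

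**What a null result could show.** At HR 1.5 the high-group proportion is 1 − 0.95^1.5 = 7.4%. Events are 49.6 and power is 29.7%, so such an effect would be missed about 70% of the time. If the true HR is 1 and 5% bleed in both groups (800 × 0.05 = 40 events), the expected 95% interval is exp(±1.96 × 2/√40) = 0.54 to 1.86. With 58 events it is 0.60 to 1.67.

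None of these figures allows for attrition or for the exclusion of subjects without a baseline FcγRIIa value (SAP 5.9). Either would lower the power.

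**The case against.** The strongest defence is that the sponsor meant 5% per year. The protocol plans ischemic events on a yearly basis ("Based on an annual ischemic event rate of 10" per cent) and allows participation of up to three years, and the annual reading passes 95% at about 2.25 years. On that view the statement omits an input but is not miscalculated. This stands as a possible explanation, but not as a reading of the text. The 5% is expressed as a share of subjects, in the same form as the 8% for the primary endpoint in the same paragraph, and the yearly ischemic rate is labelled as yearly. The planned accrual and minimum follow-up also give a mean of two years, not 2.25. At a 10% annual ischemic rate, about 800 × (1 − 0.9²) = 152 subjects would have had an event by then, so the 80-event condition would not prolong the study.

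Second, the miss rate applies to the dichotomised comparison, while SAP 5.7.2 also plans a continuous model, which is more efficient. If FcγRIIa (suitably scaled) is normal, its effect log-linear, and a median split gives HR 1.93, the log hazard ratio is about 0.41 per SD. Power is then about Φ(0.41 × √57.7 − 1.96) = 88%. This is fair, but it rests on assumptions not in the documents, it is still below 95%, and the plan states its power for high versus low.

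Third, bleeding power sets neither the sample size nor the duration, and the objective itself is worded neutrally. Both are true, and they limit the consequence to interpretation. The bleeding analysis also reuses the primary model, for which SAP 5.7.1 names an estimate, interval and p-value. That settles what is reported, not how a non-significant result is read.

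Finally, Protocol 9.4.3 plans a binary bleeding analysis without limiting it to the optimal cut, so the 1,750 comparison could be read as covered. SAP 5.7.2 nevertheless names only the optimal cut, so this part is a clarification.

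**Conclusion.** The power statement is wrong as written. On its stated inputs, power for a bleeding hazard ratio of 1.93 is about 70% with about 58 expected events, against about 120 needed for 95%. The conclusion assumes that the 5% is a proportion over the study, that 800 is the total, and that hazards are proportional. It is insensitive to the unstated split (66% to 71% for 40% to 60% high) and to the choice of formula. It is sensitive to the time base: an annual 5% would bring power to about 93% at the planned mean follow-up. The missing time base is therefore the key omission, and both readings call for an edit.

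The reading rule is a separate gap. Even at 95% power, a non-significant p-value would not establish absence of association, so the rule is needed whatever the power is. The study's size, duration and primary analysis are unaffected. This should be fixed, but it does not threaten the study.

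**What to change.** 1. **Protocol 9.2 and SAP 5.10.** State the time base of the 5%, the assumed high/low split, the expected number of bleeding events and the formula, and restate power to match. If the 5% is over the study, give about 70% for HR 1.93, with 95% reached only at an HR of about 2.4. If 95% for HR 1.93 is to stand, give the low-group proportion over follow-up that it requires (about 10.4% to 11.1%).

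2. **SAP 5.7.2, reading rule.** Add, for example: *A non-significant bleeding result alone will be reported as inconclusive, and the hazard ratio will be interpreted through its 95% confidence interval. Any margin for concluding no association will be justified in advance for a named model.* The design value of 1.93 should not become that margin by default.

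3. **SAP 5.7.2, cut-point.** Report the high-versus-low bleeding comparison at the pre-specified 1,750 cut, alongside the continuous and optimal-cut models.

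The cost is wording in two documents and one extra model run, with no new data or subjects. The downside for the sponsor is a lower stated power, if the 5% is over the study, and a more cautious conclusion on bleeding.
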